The baseline and follow-up visit includes internal vaginal pressure-pain threshold testing, which is similar in nature to the pelvic floor portion of a gynecological exam. Thus, for participants who have never had a gynecological exam, a study nurse or study doctor may complete a simple exam of the pelvic floor at the screen to promote understanding of the internal vaginal pressure-pain threshold testing that will be completed at the baseline and follow-up visit. This ensures that the integrity of our data is not biased by unfamiliar experience. Participants will be asked whether they have ever had a gynecological exam on the phone screen and a simple exam of the pelvic floor for those that say they have never had an exam will be scheduled into their screen.

Creatinine Test:

A creatinine test will be conducted to check for kidney function for all participants. This will be done via blood draw at the screen visit.

Menstrual Diaries:

All participants will be asked to complete daily diaries for a full menstrual cycle to assess their baseline scores.

[figure not shown]
Baseline Visit:

A baseline visit will be performed for all participants that have not conducted an assessment visit for EH13-094 in the last 12 months: **[Note all of these assessments are the same as the assessments approved in EH13-094]**. The baseline visit will be scheduled to occur during the luteal phase (15 to 25 days after the start of the prior menstrual cycle). Participants will be asked to confirm that menstrual pain or bleeding has not started during the baseline visit.

Food: Baseline Visits are very long so we will offer snacks to the participants (e.g., teddy grahams and fruit roll-ups).

Instrumentation: During the baseline visit, EMG and EKG electrodes, and respiratory rate monitors will be applied and information will be recorded throughout the visit. EMG leads will be placed on the lower abdomen during the bladder testing to measure muscular recruitment. The abdominal EMG leads will be moved to the knees once the bladder pain test is completed. The EKG leads and respiratory belt are placed to measure autonomic activity. The autonomic activity will be recorded to verify nociceptive experience. During each testing session, participants will also have their blood pressure and pulse taken.

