Participants will be instructed on usage of prophylactic and recommended dosage of naproxen. Participants will be instructed to take one Naproxen (500 mg) pill in the morning and one again 12 hours later the first day before their anticipated first day of menses. The research coordinators will help interpret the menstrual pain calendars for the participants to predict their next menstrual cycle. Participants will continue to take a pill twice daily for the first 3 days of their menstrual period. If participants still have menstrual pain the following day, they will be instructed to continue taking 2 pills a day until their pain stops. Any unrelieved pain can be treated with acetaminophen (according to directions listed on the package). Participants will continue taking pills before and during their period for 6-8 months until the follow up visit is performed. In the event that a participant has been taking Naproxen for 3 consecutive days and has been asymptomatic (i.e., not started their menses) we will have them stop taking the study medication. The research staff will instruct them to start taking it again as soon as they start their period.

The dosage does not exceed the maximal daily recommended over the counter dose for Naproxen (1500 mg first day, 1000 mg subsequent days).

Between visit measurements:

Diaries: On each day of menstrual bleeding and/or pain, participants will complete a daily diary. The daily diary will be completed using REDCap and asks them to rate their menstrual, bladder, and bowel pain (using a numeric rating scale where 0-no pain, 10-worst pain imaginable), describe any bleeding, and what time the study medication was taken. They will be asked to record any other pain reliever/medication they tried that day (heat pads, muscle relaxers, herbal teas, etc) in the notes section. They will be instructed to not take any additional painkillers except acetaminophen during their menses or while taking the study medication. Outside of their menses, they can treat their pain however they normally would (flu, headache). To protect confidentiality, subjects will not enter identifying information and only use their assigned subject ID #.

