Urine: Participants will be told that urine samples will allow us to verify they are taking the study medication as directed. Participants will be asked to freeze urine collected from the evening of day 2 of their menses for each cycle. 6 storage vials will be provided. The urine samples will allow us to verify if participants are taking the provided pills.

Blood: Participants will be instructed to arrive at Evanston Hospital for a scheduled blood draw 1.5-3 hours after ingesting naproxen pills. This will allow us to verify naproxen is sufficiently absorbed to provide therapeutic effects. Only one naproxen absorption blood draw will be performed per participant. Participants will be allowed to choose the most convenient period day for testing, but cannot come on the first day.

Follow up visit:

Six to eight months later, participants will be invited to return for a follow-up visit. Participants will perform the same measurements obtained in the original baseline visit. In the event participants are unable to return for a complete baseline visit, participants will receive a prorated stipend for partial

completion of items (including questionnaires). Participants will bring in any unused study medication to this visit.

Power Analysis/Data Analysis:

The primary outcomes are menstrual pain and bladder pain. Menstrual pain will be evaluated by comparing diary data and questionnaire data from baseline to 6-8 months after treatment. We estimated the needed sample size with a power analysis. Historically, the effects of NSAIDS are known to have a large effect size ($dz > .7$). A power analysis ($\alpha=.05, 1-\beta=.80$) suggests that to detect a more moderate effect of $dz=.7$ sample size of 20 would be needed. To account for a ~20-30% drop out rate, we will recruit 30 participants.

An additional primary outcome is bladder pain as measured by the experimental bladder pain test and the GUPI questionnaire. We estimated the needed sample size with a power analysis. The effects of oral contraceptives on bladder pain had enormous effect size ($dz=2.9$). Unfortunately, too few participants were willing to take oral contraceptives. A power analysis ($\alpha=.05, 1-\beta=.80$) suggests that to detect a more moderate effect of $dz=1$ sample size of 10 would be needed. We will attempt to attain a sample size of $n=20$ to allow detection of and even lower effect size $dz=0.7$ (per the primary outcome for menstrual pain).

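### The treatment-period diary has no entry on symptom-free pre-menses dosing days, so the prophylactic dose is not dated and a pain-free day cannot be told from a missed one

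*Combined protocol and SAP*

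**What the plan says.** Under Menstrual Diaries, the baseline rule is: "All participants will be asked to complete daily diaries for a full menstrual cycle to assess their baseline scores". Under Between visit measurements (Diaries), the treatment rule is: "On each day of menstrual bleeding and/or pain, participants will complete a daily diary". The treatment diary collects 0-10 ratings of menstrual, bladder and bowel pain, and asks participants to "describe any bleeding, and what time the study medication was taken".

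Under Naproxen, participants take one pill in the morning and "one again 12 hours later the first day before their anticipated first day of menses". The same section provides for a late period, where a participant has been "taking Naproxen for 3 consecutive days and has been asymptomatic (i.e., not started their menses" (the source closes the bracket here); staff then tell her to stop until bleeding starts.

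Three other checks bear on adherence. Participants "freeze urine collected from the evening of day 2 of their menses for each cycle". A blood sample is taken on a period day other than the first: "Only one naproxen absorption blood draw will be performed per participant". At the follow-up visit: "Participants will bring in any unused study medication to this visit".

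Power Analysis/Data Analysis makes menstrual pain a primary outcome, comparing diary and questionnaire data at baseline with those after 6-8 months. It does not name a diary summary (peak, mean or sum) or the days that count.

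**The concern.** The opening rationale is that naproxen given before the COX-2 cascade starts works better than naproxen given afterwards. The day before menses is therefore the day on which exposure most needs documenting, and it is also a day that will often have neither bleeding nor pain. Under the treatment rule such a day has no entry and no dose time. Without it, the sponsor cannot show which cycles were treated prophylactically and which only once symptoms had begun.

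A second problem follows. On a non-bleeding day, recording depends on the outcome: a painful day is entered and a pain-free day is not. A blank may mean no pain, or it may mean a forgotten entry. If the menstrual score averages recorded days, treatment success before menses removes its own zero from the average.

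**Working it through.** **1. The plan's own figure.** The stated sample size is 20 for dz = 0.7, alpha 0.05 and 80% power. A two-sided paired t-test gives n = 19, and n = 20 has 84.4% power. Allowing for dropout, 20/0.80 = 25 and 20/0.70 = 28.6, so 29; recruiting 30 covers both. This point leaves the sample size untouched.

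**2. What the treatment rule records.**

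| Day on treatment | Entry required? | Dose time captured? |
|---|---|---|
| Bleeding, pain | Yes | Yes |
| Bleeding, no pain | Yes, as 0 | Yes |
| Pre-menses dosing day with pain | Yes | Yes |
| Pre-menses dosing day, no pain | No | No |
| Up to 3 dosing days before a late period, no pain | No | No |

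**3. Whether another check dates the missing dose.** The urine sample is from day 2 of menses. The single blood draw is on a later period day. Returned pills give a total at the end of treatment, with no dates. None dates the pre-menses dose.

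**4. Upper bound on undated cycles.** Assume one cycle a month for 6 to 8 months and 20 completers: 20 × 6 = 120 and 20 × 8 = 160 participant-cycles. This maximum takes every cycle to have a symptom-free pre-menses dosing day. Cycles with pain that day or with early bleeding reduce it.

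**5. Effect on the pain score.** The documents give no daily pain data, so all scores here are assumed, with a 28-day cycle and zero pain outside the listed days.

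Example A covers day -1 and five bleeding days. Baseline is 3, 6, 6, 4, 2, 1 (sum 22). Treated is 0, 3, 3, 1, 0, 0 (sum 7). The treated diary holds the five bleeding days, two of them zeros, but not day -1.

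| Summary | Baseline | Treated | Fall |
|---|---|---|---|
| Same 6 days (truth) | 22/6 = 3.67 | 7/6 = 1.17 | 2.50 |
| Bleeding days only | 19/5 = 3.80 | 7/5 = 1.40 | 2.40 |
| Peak | 6 | 3 | 3 |
| Sum, blanks as zero | 22 | 7 | 15 |
| Mean of recorded days, bleeding/pain rule in both periods | 22/6 = 3.67 | 7/5 = 1.40 | 2.27 |
| Mean of all diary days, 28 against 5 | 22/28 = 0.79 | 7/5 = 1.40 | -0.61 |

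The bleeding-day mean, the peak and the sum equal what a complete diary would give. Only the last two rows are distorted.

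Example B adds one further painful non-bleeding day at each end. Baseline is 2, 3, 6, 6, 4, 2, 1, 1 (sum 25). Treated is 0, 0, 3, 3, 1, 0, 0, 0 (sum 7). The true 8-day fall is 25/8 - 7/8 = 2.25. The mean of recorded days under one rule gives 3.125 - 1.40 = 1.725. The 28-against-5 mean gives 0.89 - 1.40 = -0.51. The bleeding-day fall is again 2.40.

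With no treatment effect (Example A's baseline scores in both periods), the mean of all diary days gives 0.79 against 22/6 = 3.67, a spurious rise of 2.88. With the bleeding/pain rule in both periods, the difference is zero.

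**The case against.** The strongest objection is that the bias is not shown. The plan never says it will average recorded days. Eligibility is framed as pain of at least 5 on at least one day, which is nearer to a peak than to a full-cycle mean. With an adherent diarist, a blank under a bleeding-or-pain rule means zero, and entering that zero restores the true score. This stands: a reader might infer that the primary menstrual result is biased, but the documents do not support that, because they do not fix the summary.

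A reader might also infer that every pain-free day produced by treatment is lost. That is wrong, since bleeding days are entered whether or not they hurt. Nor is the prophylactic exposure absent altogether: a pre-menses dose is recorded when that day has pain or bleeding has begun.

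The baseline rule has a second reading. The treatment section uses the term daily diary for a form filled in only on bleeding or pain days, so the baseline could be one cycle of that same form. A figure after the Menstrual Diaries text is also not available. On that reading the 28-against-5 contrast disappears, but the undated dose and the 2.27-against-2.50 discrepancy remain.

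The reach is limited too. The menstrual outcome also uses questionnaires, and the bladder outcome rests on the bladder test and the GUPI. Finally, coordinators help predict the next period, so an intended start day may be known; that is not a record of a dose taken.

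**Conclusion.** The point holds in a limited form. Followed as written, the treatment diary leaves symptom-free pre-menses dosing days without an entry, so the prophylactic dose is undated there and a true zero is indistinguishable from a missed entry. That does not depend on which pain summary is chosen, and it cannot be repaired after the data are collected. It affects at most 120 to 160 participant-cycles under the assumptions of 20 completers and monthly cycles.

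Bias in the menstrual pain comparison is possible but not established. It ranges from none (peak, bleeding-day mean, or sum with blanks as zero) through modest understatement (2.27 for 2.50, or 1.725 for 2.25) to a reversed sign if all baseline diary days are averaged. In these assumed examples the distortion works against the drug. The two diary rules should be reconciled, and the cheap remedy is worth making before data collection.

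**What to change.** Require one REDCap diary entry, with zero allowed, on every study-medication day and every day of bleeding or pain, from the first study-medication day of the cycle through the last day of bleeding, pain or medication.

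In Power Analysis/Data Analysis, name the menstrual pain summary and compute it over the same days at baseline and on treatment. If the day before menses is included, state how cycles with no entry for that day are handled, whether because menses came early or because medication had already been stopped for a late period. State in Menstrual Diaries whether the baseline diary is kept every day of the cycle.

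The cost is a change to the REDCap trigger and about one to three short extra entries per participant per cycle. No change to dosing is implied.

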dysmenorrhea promote cross-organ or central sensitization. This is supported by clinical observations¹⁷ and experimentally in animal models of provoked uterine inflammation.⁶ Mechanisms involved in central pain modulation can be evaluated with conditioned pain modulation and pressure pain testing^{10,18} and both will be used in this proposal. Additionally, we will look at neural mechanisms using audio and visual tasks¹⁹ with EEG. We will determine whether baseline mechanisms are correlated with menstrual and bladder outcomes. The within subject design also allows us to determine if changes in mechanisms (baseline vs repeat visit) are associated with better outcomes.

Study participants

Inclusion Criteria:

Reproductive-age women (age 18-45) with dysmenorrhea will be recruited. Cases will have: a) average menstrual pain $\geq 5/10$ (0=no pain and 10=the worst imaginable pain) on at least one day during menses or during withdrawal uterine bleeding from cyclic OCs without painkillers, b) menstrual pain in the region between the umbilicus and the perineum, above the level of the inguinal ligament, and c) indication the participant has attempted to resolve pain by medical means (including NSAIDs and/or OCPs). In the circumstance that a participant originally assigned to the dysmenorrhea group does not reach a pain of 5 on any days on the daily diary, this will be handled on a case-by-case basis particularly if they used a continuous around-the-clock, effective pain treatment regimen. Participants who endorse bladder symptoms (subclinical urgency, frequency, bladder pain) on the phone screen or bladder symptoms as reported in EH13-094 will be preferentially recruited (at least 50% of enrolled participants); those who do not endorse bladder symptoms may be determined ineligible. They must not have a formal urological diagnosis such as overactive bladder or painful bladder syndrome.

Exclusion criteria:

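### Two adjacent painkiller instructions contradict each other on study-drug days outside menses, and a participant following the second could add an NSAID to study naproxen

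*Combined protocol and SAP*

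**What the plan says.** All but one of these statements are in the combined protocol and SAP under Naproxen and Between visit measurements (Diaries).

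- **Start of dosing.** The schedule reads: "take one Naproxen (500 mg) pill in the morning and one again 12 hours later the first day before their anticipated first day of menses". They then take a pill twice daily for the first three days of the period.
- **Late menses.** The rule for this case reads, in part: "taking Naproxen for 3 consecutive days and has been asymptomatic (i.e., not started their menses) we will have them stop taking the study medication". Dosing resumes when bleeding starts.
- **Continuing pain.** If menstrual pain persists after that, "they will be instructed to continue taking 2 pills a day until their pain stops".
- **Cited naproxen maximum.** "The dosage does not exceed the maximal daily recommended over the counter dose for Naproxen (1500 mg first day, 1000 mg subsequent days".
- **First painkiller instruction (Diaries).** "They will be instructed to not take any additional painkillers except acetaminophen during their menses or while taking the study medication".
- **Second painkiller instruction, the next sentence.** "Outside of their menses, they can treat their pain however they normally would (flu, headache".

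Separately, Inclusion Criteria item (c) requires "indication the participant has attempted to resolve pain by medical means (including NSAIDs and/or OCPs".

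**The concern.** The first painkiller instruction applies on two kinds of day: days of menses and days on study drug. The second applies on every day outside menses. A study-drug day before bleeding starts, or after it ends, falls under both, and they disagree. The regimen produces such days by design, because the strategy under test is prophylactic dosing before menses.

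A woman with a headache on her first pill day, not yet bleeding, can read the second sentence as permission to take whatever she usually takes. Item (c) of the inclusion criteria lists NSAIDs among the treatments participants may have tried, so an NSAID is a plausible choice, though the documents do not say what participants use for headache or flu.

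Two things are at stake. The first is participant safety: the exclusion criteria and the screening creatinine test show that the protocol treats naproxen exposure as something to guard. The second is clarity about what was taken on the prophylactic day, which is the exposure the study sets out to evaluate.

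**Working it through.** **Step 1. Which instruction applies on which day.**

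| Day | First sentence | Second sentence | Result |
|---|---|---|---|
| In menses, on study drug | acetaminophen only | does not apply | consistent |
| In menses, off study drug | acetaminophen only | does not apply | consistent |
| Outside menses, off study drug | does not apply | usual treatment | consistent |
| Outside menses, on study drug | acetaminophen only | usual treatment | **conflict** |

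**Step 2. When the fourth row occurs.**

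- Planned: one day per cycle, the day before expected menses.
- Late menses: up to three consecutive days, after which the drug is stopped. Because it restarts with bleeding, the restart adds no conflicting day.
- Pain continuing after the third day of the period: possibly further days, if pain outlasts bleeding. The document gives no figure for this.
- Early menses: none before bleeding, because dosing is timed to the predicted date. One day per cycle is therefore the planned number, not a minimum.

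To give a scale, assume 28-day cycles (not stated in the document) over the 6 to 8 months of treatment, taken as 182.6 to 243.5 days:

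- Cycles: 182.6 / 28 = 6.5 to 243.5 / 28 = 8.7.
- One day per cycle as planned: about 6.5 to 8.7 days per woman.
- Three days per cycle, if every period were late: 3 x 6.5 = 19.5 to 3 x 8.7 = 26.1 days. This is an extreme case. Coordinators help predict the cycle, and women without regular menses are excluded.

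**Step 3. Study dose against the cited naproxen figures.** Inputs from the Naproxen section: two 500 mg pills a day; 1500 mg cited for the first day and 1000 mg for later days.

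- Study dose: 2 x 500 = 1000 mg a day.
- First dosing day: 1500 - 1000 = 500 mg below the cited figure.
- Later dosing days: 1000 - 1000 = 0 mg, equal to the cited figure.

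The document's statement that the regimen does not exceed the maximum is therefore reproduced.

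**Step 4. Conflicting days before menses at the cited figure.** With k such days in a cycle, the number at the figure is k - 1: 0 of 1, 1 of 2, or 2 of 3. Any study-drug day after bleeding ends would also be at the figure.

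Steps 3 and 4 take *first day* to mean the first dosing day of each cycle. If it meant only the first day of dosing in the whole study, the planned day before menses would be at the figure in every later cycle.

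**The case against.** The best defence is that the two sentences can be harmonised. The reference to study medication in the first sentence adds something only on study-drug days outside menses, so it was evidently written with those days in mind. The second sentence reads as a general contrast with examples of unrelated pain, and a specific rule would normally prevail over a general one. This is a plausible account of what was intended. But the second sentence does not say it, it comes last, and a participant cannot be expected to apply a rule of construction. The contradiction in the text remains.

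Other objections succeed, and they limit what can be claimed. A reader might infer any of the following, and the documents do not support them:

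- *That the study dose is already at the cited maximum on the planned day before menses.* On the per-cycle reading of *first day* it is 500 mg below.
- *That an added product would falsify the protocol's statement about dose.* That statement describes the study regimen, which meets it. It makes no promise about total intake.
- *That any added NSAID can be judged against the cited figures.* They are for naproxen only. The documents give no combined limit for other NSAIDs.
- *That the menstrual-pain result is biased.* During menses the second sentence does not apply and the rule is acetaminophen only. The documents give no basis for the size or direction of any effect from an occasional tablet before menses.
- *That extra painkiller use cannot be totalled.* Participants are asked to record other pain relievers in a notes section. The diary form is not in the documents, so whether it asks for amounts is unknown.

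**Conclusion.** The text is wrong as written: an internal contradiction of low to moderate severity. On study-drug days outside menses, one sentence bars painkillers other than acetaminophen and the next permits usual treatment. This affects one planned day per cycle, up to three if menses is late, and possibly days after bleeding ends.

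On such days after the first dosing day, the 1000 mg study dose already equals the cited naproxen figure. On the first dosing day it is 500 mg below. Those comparisons rest on reading *first day* as the first dosing day of a cycle and bear directly only on added naproxen. The contradiction itself depends on neither assumption. How often participants would act on the second sentence, and what that would do to the menstrual-pain outcome, cannot be determined from the documents.

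**What to change.** The investigator should reconcile the two sentences so that a single instruction applies to every study-drug day, whether or not the participant is bleeding, and use the same wording in the participant instructions. Which rule to adopt is a clinical decision, and this review takes no view on it. The cost is about one sentence in the protocol and the matching line in the participant instructions.

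Optionally, the diary could ask for the product and amount of any other painkiller on every study-drug day. The protocol requires diary entries only on days with bleeding or pain, so a symptom-free study-drug day before menses may have no entry, and it does not state that amounts are requested. This would take a few REDCap fields. It is a useful addition, but the point does not depend on it.
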